#### **7.2.6. COUNTING RULES FOR OCCURRENCES OF SOLICITED ADVERSE EVENTS**

When the occurrences of solicited adverse events are summarized, each event recorded as having occurred during a specific period will be counted as only one occurrence regardless of the number of days on which it occurs.

For a given subject and the analysis of solicited symptoms within 7 days post-vaccination, missing or non-evaluable measurements will not be replaced. Therefore the analysis of the solicited will include only vaccinated subjects for doses with documented safety data (i.e., symptom screen completed). More specifically the following rules will be used:

- Subjects who documented the absence of a solicited symptom after one dose will be considered not having that symptom after that dose.
- Subjects who documented the presence of a solicited symptom and fully or partially recorded daily measurement over the solicited period will be included in the summaries at that dose and classified according to their maximum observed daily recording over the solicited period.
- Subjects who documented the presence of a solicited symptom after one dose without having recorded any daily measurement will be assigned to the lowest intensity category at that dose (i.e. 38°C for fever or grade 1 for other symptoms).
- Doses without symptom sheets documented will be excluded.

#### **7.2.7. GEOMETRIC MEAN TITERS (GMTs)**

Geometric Mean Titer (GMT) calculations are performed by taking the inverse logarithm of the mean of the log titer transformations. Antibody titers below the cut-off of the assay will be given an arbitrary value of half the cut-off of the assay for the purpose of GMT calculation. The cut-off value will be defined by the laboratory before the analysis.

## **8. OUTPUT PRESENTATIONS**

The templates provided with this SAP describe the presentations for this study and therefore the format and content of the summary tables, figures and listings to be provided by IQVIA Biostatistics.

Some minor modifications may be necessary to the planned design of tables, figures, and listings to accommodate data collected during the actual study conduct.

---

Document:	\\\usadc-nas01a\cp_ops\PROJECTS\Glaxo SmithKline\GSK208109_BZA47109\SAP		
Author:	PPD	Version Number:	3.0
		Version Date:	27SEP2021

Template No: CS\_TP\_BS016 – Revision 5  
Effective Date: 01Apr2018

Reference: CS\_WI\_BS005

---

## 9. DISPOSITION AND WITHDRAWALS

All subjects who provide informed consent will be accounted for in this study. Subject disposition will be tabulated for each study treatment and for all subjects combined with the number of subjects who are randomly assigned to treatment, complete the study, prematurely discontinue, and the reason for early discontinuation. A listing will present dates of completion or early withdrawal and the reason for early discontinuation, if applicable, for each subject.

Listings of inclusion/exclusion criteria responses, study protocol deviations, treatment randomization and study treatment administration will be provided.

A listing of subjects whose trial participation was impacted by COVID-19 will be presented along with the description of the impact. Number of subjects who discontinued study drug or study due to COVID-19 infection or issues related to the COVID-19 pandemic will be summarized.

## 10. DEMOGRAPHIC AND OTHER BASELINE CHARACTERISTICS

Individual subject demographics and baseline characteristics (medical history and results from pregnancy tests) will be presented in listings.

Demographic characteristics such as age, sex, race, ethnicity, height, weight, and body mass index (BMI) will be summarized and tabulated by treatment and for all subjects overall. Descriptive statistics (mean, median and standard deviation) will be presented for age, height, weight, and BMI. Frequency counts and percentages will be presented for sex, race, ethnicity, age group (50-59 years old and 60-70 years old) and step.

No statistical testing will be carried out for demographic or other baseline characteristics.

## 11. PROTOCOL DEVIATIONS

### 11.1. DEVIATIONS RELATED TO STUDY CONDUCT

A protocol deviation is any noncompliance with the clinical trial protocol, good clinical practice (GCP), or Manual of Procedure requirements. The noncompliance may be either on the part of the subject, the site PI, or the study site staff.

Any subject enrolled who does not meet eligibility criteria will be considered an enrollment deviation. Protocol deviations will be listed including a classification of minor, major, or critical as determined by clinical staff. Any protocol deviation related to study conduct that is assessed as COVID-19 related will be clearly identified in the outputs and clinical study report.

---

Document:	\\\usadc-nas01a\cp_ops\PROJECTS\Glaxo SmithKline\GSK208109_BZA47109\SAP		
Author:	PPD	Version Number:	3.0
		Version Date:	27SEP2021

Template No: CS\_TP\_BS016 – Revision 5  
Effective Date: 01Apr2018

Reference: CS\_WI\_BS005

## 11.2. DEVIATIONS RELATED TO IMMUNOGENICITY ANALYSIS

Changes to the procedures or events, which may impact the quality of the immunogenicity data, will be considered significant protocol deviations and will be described within the clinical study report. These changes or events will include any circumstances that will alter the evaluation of the immunogenicity results. Examples include, but may not be limited to, sample processing errors that lead to inaccurate immunogenicity results, and/or inaccurate dosing.

Subjects may be eliminated from the per-protocol Set for analysis of immunogenicity if, during the study, they incur a condition that has the capability of altering their immune response or are confirmed to have an alteration of their initial immune status. Subjects may also be eliminated from the per-protocol set based on usage of certain concomitant medications/products/vaccines as described in Section 6.8.2 of the protocol. Such scenarios will be discussed by the study team and decision to exclude a subject and/or data from the Per-protocol analysis set (Day 61, Day 180 and Day 390) or subcohort per-protocol analysis set (Day 521 and Day 670) will be taken on a case-by-case basis.

Other deviations (not a comprehensive list) leading to elimination from the per-protocol set are:

- Invalid informed consent
- Fraudulent data
- randomization code broken
- dose volume insufficient
- vaccination not according to protocol
- vaccine dose storage conditions (temperature deviation)
- vaccine administered out of expiry date
- violation of inclusion/exclusion criteria
- interval between doses
- interval between post vaccination blood sampling and previous dose
- two doses not in the same treatment group
- concomitant infection related to study vaccine or not related to study vaccine that may alter the immune response
- serology result at post vaccination dose 2 not available for all assays (blood sample not available or result not available)

Protocol Deviation Management Plan (PDMP) describes the complete list of elimination codes that could lead to exclusion from the per-protocol set.

---

Document:	\\\usadc-nas01a\cp_ops\PROJECTS\Glaxo SmithKline\GSK208109_BZA47109\SAP		
Author:	PPD	Version Number:	3.0
		Version Date:	27SEP2021

Template No: CS\_TP\_BS016 – Revision 5  
Effective Date: 01Apr2018

Reference: CS\_WI\_BS005

## 12. MEDICAL HISTORY

Medical History coded using MedDRA Version 22.0 will be presented for the exposed set. Medical history for subjects assessed as probable, confirmed or suspected case of COVID-19 will be summarized.

## 13. MEDICATIONS

Medication usage coded using the GSK Drug Dictionary Version 1.6 will be presented for the exposed set.

- 'Prior' medications are medications which started and stopped prior to the first dose of study treatment.
- 'Concomitant' medications are medications which were taken during the treatment period, or specifically:
  - started after the first dose of study treatment or
  - started prior to the first dose of study medication and were continued after the first dose of study treatment

The percentage of subjects using concomitant medications (any medication, any antipyretic and any antipyretic taken prophylactically, respectively) during the 7-day follow-up period and during the 30-day follow-up period will be summarized by group after each vaccination and overall.

## 14. STUDY MEDICATION EXPOSURE

Exposure to study treatment as the number of doses administered will be presented for each treatment. Exposure for subjects assessed as probable, confirmed or suspected case of COVID-19 will be summarized separately.

## 15. IMMUNOGENICITY ANALYSIS

The primary analysis will be based on the Per-protocol Set for analysis of immunogenicity. If, in any study group, the percentage of vaccinated subjects with serological results excluded from the Per-protocol Set for analysis of immunogenicity is 10% or more, a second analysis based on the Full Analysis Set will be performed.

The analysis of subjects receiving Dose 3 on an active arm will be based on the Subcohort Per-protocol Set for analysis of immunogenicity.

Numerical serology results will be derived from the content of IS.ISORRES in the SDTM dataset. For

Document:	\usadc-nas01a\cp_ops\PROJECTS\Glaxo SmithKline\GSK208109_BZA47109\SAP		
Author:	PPD	Version Number:	3.0
		Version Date:	27SEP2021

Template No: CS\_TP\_BS016 – Revision 5  
Effective Date: 01Apr2018

Reference: CS\_WI\_BS005

assays with a specific cut-off, the following derivation rules apply:

IS.ISORRES	Derived value
“< value” and value is <= assay cut-off	cut-off/2
“< value” and value is > assay cut-off	value
“> value” and value is < assay cut-off	cut-off/2
“> value” and value is >= assay cut-off	value
“value” and value is < cut-off	cut-off/2
“value” and value is >= cut-off	value
All other cases	missing

The following immunogenicity variables will be assessed:

- Anti-Toxin A neutralizing antibody titers (using HT29 cell line)
- Anti-Toxin B neutralizing antibody titers (using HCT116 cell line)

A listing of collection dates and times for the immunogenicity variables will be presented for subjects within each treatment group. For each test method, the neutralizing antibody titers from TNA assay will be listed and summarized by treatment groups across all scheduled timepoints during entire study.

For each study group, each age group (18-45 Y versus 50-70 Y) and/or subcohort (as applicable), at each timepoint that blood samples are collected for humoral immune response and for each assay:

- Percentage of subjects above the assay cutoff with their exact 95% CI will be tabulated
- Geometric mean titers and their 95% CI will be calculated
- Geometric mean fold-rise with their exact 95% CI will be tabulated
- Percentage of subjects with >=2, 4, 8, 16, 32, 64 fold-rise from baseline for each assay
- Percentage of subjects with >=2, 4, 8, 16, 32, 64 fold-rise from baseline for both anti-Tox A and anti-Tox B for neutralizing titers
- Antibody titers will be investigated using Reverse Cumulative Curves

The same tabulations will be performed by age 50-59 Y versus 60-70 Y and by serostatus at baseline (above or equal to cut-off versus below the cut-off) [if at least 6 subjects are available in these sub-group and in at least one active arm]

Linear mixed model with repeated measures will be used to perform pairwise comparison between groups in anti-toxin A neutralizing antibody titers and anti-toxin B neutralizing antibody titers at Day

---

Document:	\\usadc-nas01a\cp_ops\PROJECTS\Glaxo SmithKline\GSK208109_BZA47109\SAP		
Author:	PPD	Version Number:	3.0
		Version Date:	27SEP2021

---

Template No: CS\_TP\_BS016 – Revision 5  
 Effective Date: 01Apr2018

Reference: CS\_WI\_BS005

31, Day 61, Day 180 and Day 390. The model will use fixed effects for treatment, time point, step, treatment×time point, baseline value as covariate, and a repeated time point effect within a subject under a unstructured covariance matrix. Variance between the groups will not be considered equal. Age and gender will be included in the model as covariates if the data allow. Additional covariance structures and suitable transformation (e.g. log) may be explored to attain convergence and meet model assumptions, respectively. This analysis will be performed on the age stratum 50-70 year old adults.

A similar linear mixed model will be used to evaluate the difference between treatments for subjects who received the 3rd dose except the model will not include a fixed effect for step. CCI [REDACTED]

Descriptive summaries planned for immunogenicity variables (titers) described above will additionally be presented for COVID-19 analysis set.

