## 6.1. SUMMARY STATISTICS

For qualitative variables, the population size (N for sample size and n for available data) and the percentage (of available data) for each class of the variable will be presented. Quantitative variables will be summarized using descriptive statistics, including N (with data available), Nmiss (with missing data), mean, standard deviation (SD), coefficient of variation (CV%), median, Q1, Q3, minimum, and/or maximum values. Geometric mean will be included for immunogenicity parameters, where applicable. Coefficient of variation will not be presented for change from baseline results.

The exact two-sided 95% CIs for a proportion within a group will be calculated using the Clopper-Pearson exact method.

The geometric mean antibody titers (GMTs) calculations will be performed by taking the anti-log of the mean of the log10 titer transformations. Confidence interval for geometric means will be derived by raising 10 to the confidence interval associated with mean of log10 values i.e. CI of geometric mean =  $10^{(CI \text{ for the mean of log10 values})}$ . All subjects with data will be considered. Subjects whose antibody titers are below the cut-off of the assay will be given an arbitrary value of half the cut-off for the purpose of GMT calculation.

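### A serology result reported as '< value' with the value above the assay cut-off is set to that value, which biases the titer upward and always counts the subject as above the cut-off

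*SAP*

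**What the plan says.** SAP Section 15 states: "Numerical serology results will be derived from the content of IS.ISORRES in the SDTM dataset". A table then converts each reported string to a number for assays with a cut-off. Two of its rows matter most here:

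- '< value' "and value is <= assay cut-off": the derived value is cut-off/2.
- '< value' "and value is > assay cut-off": the derived value is the reported value itself.

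A parallel row sets '> value' with the value below the cut-off to cut-off/2. Anything the table does not list becomes missing.

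The derived numbers feed the whole immunogenicity analysis. Section 15 states: "Percentage of subjects above the assay cutoff with their exact 95% CI will be tabulated". It also plans GMTs, geometric mean fold-rises, six fold-rise thresholds, reverse cumulative curves, subgroup tables by baseline serostatus, and a mixed model with the baseline value as covariate. SAP Section 6.6 defines the immunogenicity change from baseline as the later value divided by the baseline value.

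SAP Section 6.1 gives the general rule: "Subjects whose antibody titers are below the cut-off of the assay will be given an arbitrary value of half the cut-off". Section 7.2.7 repeats it and adds: "The cut-off value will be defined by the laboratory before the analysis". Neither section addresses a '<' result whose bound lies above the cut-off. Neither document has such results retested, treated as censored, set to missing, counted, or examined in a sensitivity analysis.

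**The concern.** A '< value' result says only that the titer lies somewhere below the bound. When the bound is above the cut-off, the result does not show on which side of the cut-off the titer falls. The table nevertheless assigns the bound, a number that the result itself rules out, and so settles serostatus as above the cut-off every time.

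The direction of the error in the value is known:

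- **After vaccination:** the GMT and fold-rise are raised, and the percentage above cut-off may be.
- **At Day 1:** the baseline is raised, so the fold-rise is lowered, and a subject who is in fact seronegative may be tabulated as seropositive.

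The baseline split is of scientific interest in this trial. The Amendment 03 rationale in the protocol attributes the weaker anti-Toxin B response to subjects without measurable baseline antibody.

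**Working it through.** The plan gives no figure for this rule, so there is nothing to reproduce. The check applies the rule and measures its effect.

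**Inputs.** The rule is from the SAP Section 15 table. Group size n = 36 is the evaluable number per older-adult active arm in protocol Section 9.2 (45 × 0.8 = 36). The cut-off C is not given. The bound v and the number k of affected results are assumptions.

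**Step 1: the rule at several bounds.**

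| Reported | Derived | At or above C? |
|---|---|---|
| < 0.5C | 0.5C | no |
| < C | 0.5C | no |
| < 1.5C | 1.5C | yes |
| < 2C | 2C | yes |
| < 4C | 4C | yes |
| < 10C | 10C | yes |

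Every bound above C gives a derived value above C. It therefore meets both definitions in use: above the cut-off for the percentage, and at or above it for baseline serostatus. The derived value also jumps from 0.5C at v = C to just over C as soon as v exceeds C.

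**Step 2: GMT.** With value/2 as comparator, each affected value is overstated by v ÷ (v/2) = 2, whatever v is. The group GMT is multiplied by 2^(k/n):

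- k = 1: 2^(1/36) = 1.02, about 2%.
- k = 3: 2^(3/36) = 1.06, about 6%.

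**Step 3: fold-rise.** An affected post-vaccination sample doubles that subject's fold-rise and an affected Day 1 sample halves it. Either is one step on the 2, 4, 8, 16, 32, 64 scale.

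**Step 4: percentage above cut-off.** The overstatement is at most k/n, reached if all k titers are truly below C: 1/36 = 2.8 points and 3/36 = 8.3 points. It is zero if all are truly above C.

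**Step 5: small subgroups.** SAP Section 15 allows age and serostatus tables with as few as 6 subjects. One affected result among 6 gives 2^(1/6) = 1.12, a 12% shift in GMT, and up to 1/6 = 16.7 points.

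**Scale.** Protocol Table 23 gives, for an observed fold-rise of 10 with n = 36, intervals of 5.20 to 19.23 (Toxin A) and 3.36 to 29.79 (Toxin B). The upper limits are 19.23/10 = 1.9 and 29.79/10 = 3.0 times the estimate. A 2% or 6% shift is small beside either.

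**The case against.** The strongest reply is that the case may never arise. The documents give no cut-off, starting dilution or reporting range. A bound above the cut-off needs an unusual sample, for example one short of serum. Yet about 20 mL of blood is drawn per visit (protocol Section 8.8), the neutralization assays rank first and second when volume is short (Section 8.8.2), and ELISA has been dropped (SAP Section 3.3). The row may be a defensive default. This stands: the frequency is unknown and may be zero. It does not make the rule right for any result that reaches it.

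A reader might infer four stronger things that the documents do not support:

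- **An eight-fold error.** With v = 4C, comparing with C/2 gives 4C ÷ 0.5C = 8, hence GMT shifts of 8^(1/36) = 1.06 and 8^(3/36) = 1.19. That presumes the titer is below the cut-off, which a '< 4C' result does not show.
- **Certain misclassification.** The titer may be 2C or 3C, in which case counting it as above the cut-off is correct. Only the upward bias in the value is certain.
- **A contradiction with SAP Sections 6.1 and 7.2.7.** Those sections apply half the cut-off to titers below the cut-off, not to every '<' result. The table follows one crude convention: take the reported number, and replace it by half the cut-off if it does not reach the cut-off.
- **An effect on who receives Dose 3.** Eligibility in protocol Section 4.1 does not depend on serostatus, and the third dose was introduced before this SAP version. Protocol Section 9.1 states that no formal hypotheses are tested.

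It is also fair that value/2 is a convention, and that for bounds between C and 2C it falls below the cut-off while serostatus is set to missing. The number is then only a stand-in for averaging and makes no claim about serostatus. Unlike the bound, it respects what the result says, and it meets the existing C/2 row without a jump at v = C.

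**Conclusion.** The rule is wrong as written, and its practical weight is minor. For any '< value' result with the bound above the cut-off, the plan assigns a titer that the result excludes and fixes serostatus that the result leaves open. The bias in the value is always upward; error in serostatus is possible, not certain.

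Against value/2, in a group of 36, one such result shifts the GMT by about 2% and three by about 6%. The percentage above cut-off could be overstated by up to 2.8 and 8.3 points. These sizes rest on assumed counts, and the actual count may be zero. The endpoints are secondary and descriptive, and no decision rule in the documents turns on this row.

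The row for '> value' below the cut-off is a minor parallel case. Such a result is equally indeterminate for serostatus, but nothing in the documents suggests that it will occur.

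**What to change.** Amend the SAP Section 15 derivation table:

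- For '< value' with the value above the cut-off, use value/2 for GMT and fold-rise. Set serostatus to missing for the percentage above cut-off and for the baseline-serostatus subgroup.
- Send '> value' with the value below the cut-off to the table's existing missing outcome.
- Report the number of such results per arm and visit.

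SAP Section 4.4 already has all previous analyses re-produced at the final analysis, so the amended rule can apply to every timepoint.

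The cost is two table rows and one count. A few results become missing for serostatus, which matters most in subgroups close to the minimum of 6, and value/2 remains a convention. If the count is zero, no result changes.

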Results from a recent interim analysis on data from subjects immunized with 2 doses of the F2 antigen candidate (with or without the inclusion of an adjuvant), showed an acceptable safety profile for both formulations. Analysis on immunogenicity showed that an anti-toxin (A/B) neutralizing antibodies (TNA) response can be elicited by the F2 adjuvanted formulation. However, a lower immune response post second dose was observed for anti Tox B TNA in subjects who had no quantifiable antibodies at baseline, indicating that a third vaccine dose may be necessary to reach higher level of antibodies.

Published data from a Phase II study with another *Clostridium difficile* candidate¹, using full Toxin A and B aluminum-based toxoids, showed similar trend in toxin neutralization assay values post second dose, also evidencing that a third dose induced very high response in seronegative subjects.

The aim of this amendment is to offer a third dose of the vaccine to subjects recruited in the active groups of the last step of the study, to demonstrate if a similar kinetics in terms of anti-Toxin A/B TNA can be achieved with the F2 antigen formulation with or without an adjuvant. The purpose of this amendment is also to assess the safety and immunogenicity following the addition of a third dose in a subcohort of subjects aged 50-70 years, recruited in the Step 4 of the study.

The details of Clinical Laboratory Sciences, Marburg were deleted from the protocol, as it would no longer be used for the study purposes.

The COVID-19 guidance was updated to mention the most recent version applicable at the time of study conduct and the reporting period for pregnancies was updated to 24 hours from 2 weeks.

The opportunity was also taken to do minor editorial corrections for typographical, grammar, and consistency errors.

Table 3 Description of Changes in Amendment 03

Section # and Name	Description of Change	Brief Rationale
Title Page 1.1 Synopsis 1.2 Schema 4.1 Overall Design 6.1 Study Treatment(s) Administered 9.4.2.1 Primary Analyses	Added information about an additional third dose to be given to subjects on active treatment	To provide the information related to the proposed third dose
1.1 Synopsis 8.11 Study Procedures During Special Circumstances	Updated version of EMA Guidance on the Management of Clinical Trials during the Coronavirus pandemic.	To indicate the recent version, applicable to the study conduct

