### 3.3. CHANGES TO ANALYSIS FROM PROTOCOL

Given the staggered enrolment, step is used as stratification factor in the randomization algorithm. Step will be used as a covariate in the inferential analysis.

The sponsor has decided not to perform ELISA assay in the study. All references to concentrations from ELISA have been deleted from the last approved SAP in this document.

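### Does SAP Section 15 need to fix the log10 scale, and the age and gender terms, in the between-group titer models?

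*SAP*

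**What the plan says.** SAP Section 15 plans pairwise group comparisons of anti-Toxin A and anti-Toxin B neutralizing titers at Days 31, 61, 180 and 390 in the 50-70 year stratum. The mixed model has treatment, time point, step and treatment-by-time effects, with "baseline value as covariate, and a repeated time point effect within a subject" under an unstructured covariance matrix and unequal group variances. No scale is given for the titer or the baseline. The only visible statement is "Additional covariance structures and suitable transformation (e.g. log) may be explored to attain convergence and meet model assumptions, respectively". On the minimization factors it says "Age and gender will be included in the model as covariates if the data allow".

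For the third dose, "A similar linear mixed model will be used to evaluate the difference between treatments", without step. SAP 3.3 gives the reason for step in the main model: "Step will be used as a covariate in the inferential analysis".

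Other sections do give a scale. SAP 6.1 and 7.2.7 compute GMTs and their intervals from log10 means, SAP 6.6 defines immunogenicity change as post-dose over baseline, and SAP 6.3 sets the decimals for GMT ratios and their limits. For low values, "Antibody titers below the cut-off of the assay will be given an arbitrary value of half the cut-off" (SAP 7.2.7), and the derivation table in Section 15 applies the same rule to the serology results. Protocol 9.4.3.2, Between Groups Assessment, is redacted. So are the text after the Dose 3 model in SAP 15 and the whole of SAP 15.1.

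**The concern.** A model of titers can give very different answers on the raw and log scales, and the visible sentence leaves the choice open. It also does not say that the baseline is transformed along with the response. A raw baseline is dominated by a few high values and removes less residual variance, so the group contrast loses precision. An untransformed response would estimate differences in arithmetic mean titers, not the GMT ratios that SAP 6.3 formats.

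Age and gender are the minimization factors for ages 50-70 (SAP 3.4), so one would normally adjust for them without a condition. The statistical team is unblinded from the first interim analysis (SAP 4.3), so an open modelling choice looks less comfortable than usual. At stake would be the width of the interval for adjuvanted against unadjuvanted antigen, and whether results are comparable across toxins and between interim and final analyses.

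**Working it through.** **1. The plan's own figure.** Protocol Table 23 uses 36 evaluable subjects (45 × 0.8) and log10 SDs of 0.84 (Toxin A) and 1.4 (Toxin B) for the fold-rise. With t(0.975, 35 df) = 2.030, the limits are GMFR × 10^(±t × SD/√36).

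- Toxin A: 2.030 × 0.84/6 = 0.284. A GMFR of 10 gives [5.20; 19.24]; stated [5.20; 19.23].
- Toxin B: 2.030 × 1.4/6 = 0.474. A GMFR of 10 gives [3.36; 29.76]; stated [3.36; 29.79].

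The planning is on log10.

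**2. Would raw titers pass an assumption check?** For a lognormal titer, mean/median = exp(s²/2), with s = SD × ln 10. Using the fold-rise SDs as a proxy for the titer SD:

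- SD 0.84: s = 1.934, ratio about 6.5.
- SD 1.4: s = 3.224, ratio about 180.

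Residuals that skewed would fail any ordinary check, so the SAP's own clause leads to the log scale. The cost of ignoring it would be large. In a single-time-point ANCOVA simulation (36 per arm, SD 0.84, baseline SD 0.6, correlation 0.5, true GMT ratio 5, all assumed apart from n and the SD), the 95% interval excluded no difference in 97.5% of runs with log titer and log baseline, and in 47.8% with both raw. With no true difference, the raw analysis rejected in 2.5% of runs, so the error would be toward missing a difference.

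**3. Log response with raw baseline.** Assume lognormal titers, the same log10 SD at baseline and afterwards, and correlation ρ. The squared correlation between a normal variable and its exponential is c² = s²/(exp(s²) − 1). The large-sample ratio of interval widths, raw against log baseline, is √[(1 − ρ²c²)/(1 − ρ²)].

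| log10 SD | s² | c² | ρ = 0.5 | ρ = 0.7 |
|---|---|---|---|---|
| 0.5 | 1.325 | 0.480 | 1.08 | 1.22 |
| 0.84 | 3.741 | 0.091 | 1.14 | 1.37 |

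These are upper figures, with no assay floor and large samples. A simulation of the planned type of repeated-measures model (36 per active arm, Day 61) gives smaller ratios, which shrink further as more baselines are set to half the cut-off:

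| Baselines below cut-off | SD 0.5, ρ 0.5 / 0.7 | SD 0.84, ρ 0.5 / 0.7 |
|---|---|---|
| 0% | 1.063 / 1.180 | 1.103 / 1.280 |
| 50% | 1.040 / 1.102 | 1.070 / 1.172 |
| 85% | 1.005 / 1.019 | 1.018 / 1.042 |

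The documents do not give the share below cut-off, but it is not zero. The Amendment 03 rationale reports that "a lower immune response post second dose was observed for anti Tox B TNA in subjects who had no quantifiable antibodies at baseline", and SAP 15 plans tabulations "by serostatus at baseline (above or equal to cut-off versus below the cut-off". The top-right corner of the table is also a strained case. With equal variances, fold-rise SD = titer SD × √(2(1 − ρ)). A titer SD of 0.84 with ρ = 0.7 therefore implies a fold-rise SD of 0.84 × √0.6 = 0.65, not the 0.84 in Protocol 9.2.

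**4. Age and gender.** If they explain 5% or 10% of residual variance (assumed), omitting them widens the interval by 1/√0.95 = 1.026 or 1/√0.90 = 1.054. The condition reads as a feasibility guard. Four time points under an unstructured matrix need 4 × 5/2 = 10 parameters, or 30 if each of three groups has its own matrix. Protocol Table 21 expects only about 50 subjects at Days 521 and 670. Two further fixed-effect terms will rarely cause failure, so they would normally stay in.

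**5. Timing.** Amendment 03 (18 May 2021) already reports post-dose-2 immunogenicity results. SAP version 3.0 is dated 27 September 2021. Any wording added to that version would follow the Day 61 results and could at most precede the Dose 3 results.

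**The case for a change.** The best case for a change is that it costs two or three sentences and no data. The legible text does leave the scale open, SAP 3.3 calls this the inferential analysis, and nothing visible ties the GMT ratios in SAP 6.3 to the mixed model. The Dose 3 model drops step, so age and gender are its only remaining allocation factors, and they are conditional. Stating the scale before the Dose 3 results would also keep the choice the same for both toxins and both models.

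The description of the text stands, and so does the direction of the precision loss. The step from there to a defect does not. No passage suggests a raw baseline beside a log response; that pairing is conjecture. Writing the scale down now cannot remove a choice made with treatment codes known, because the Day 61 results had already been seen. The protocol abbreviation list defines ANCOVA although the term appears nowhere else in the visible protocol, which suggests that a between-group model sits in the redacted text. SAP 3.3 lists the changes from the protocol and mentions none to the scale. It cannot fairly be said that the plan lacks this statement.

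**Conclusion.** No change is needed. This is an unwritten rule that the rest of the plan settles: analysts following the SAP would log10-transform titer and baseline, apply the half-cut-off rule already set, back-transform to GMT ratios, and include age and gender unless the model fails.

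If the baseline were left raw by oversight, the Day 61 interval would be about 6 to 28% wider with no baseline below cut-off, 4 to 17% with half below, and 0.5 to 4% with 85% below. Leaving out age and gender would add roughly 3 to 5%. These figures rest on lognormal titers, log10 SDs of 0.5 to 0.84, correlations of 0.5 to 0.7 and assumed R² values; only the 0.84 comes from the protocol, where it is a fold-rise SD. Toxin B, with its larger planning SD of 1.4, is not in that table. In the single-time-point simulation at correlation 0.5, its interval factor around the GMT ratio goes from 3.74 to 4.14 with a raw baseline, against 2.20 to 2.34 for Toxin A.

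Immunogenicity is a secondary objective (SAP 2.2), Protocol 9.1 sets no formal hypotheses, and SAP 4.3 calls the analyses descriptive. The within-group GMTs, fold-rises and reverse cumulative curves do not use this model. The conclusion would be weaker if the redacted between-group text specified a raw-scale analysis, but nothing visible points that way.
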